### **5.2.10. Adequate baseline tumor assessment**

Adequate baseline is defined using the following criteria:

- All baseline assessments must be within 28 days prior to and including ‘start date’.
- All documented lesions must have non-missing assessments (ie, non-missing measurements for target lesions and non-missing lesions assessment status at baseline for non-target lesions).

### **5.2.11. Adequate post-baseline tumor assessment**

An adequate post-baseline assessment is defined as an assessment where a response of CR, PR, SD, non-CR/non-PD, or PD can be determined (see Section 6.1.2.1). Time points where the response is not evaluable (NE) or no assessment was performed will not be used for determining the censoring date.

## **5.3. Methods to Manage Missing Data**

### **5.3.1. Missing data**

Unless otherwise specified, all data will be evaluated as observed, and no imputation method for missing values will be used.

In all patient data listings imputed values will be presented. In all listings imputed information will be flagged.

Missing statistics, eg when they cannot be calculated, should be presented as 'ND' or 'NA'. For example, if N=1, the measure of variability (SD) cannot be computed and should be presented as 'ND' or 'NA'.

### **5.3.1.1. Pharmacokinetic concentrations**

#### **Concentrations Below the Limit of Quantification**

For all calculations, figures and estimation of individual pharmacokinetic parameters, all concentrations assayed as below the level of quantification (BLQ) will be set to zero. In log-linear plots these values will not be represented. The BLQ values will be excluded from calculations of geometric means and their CIs. A statement similar to 'All values reported as BLQ have been replaced with zero' should be included as a footnote to the appropriate tables and figures.

#### **Deviations, Missing Concentrations and Anomalous Values**

In summary tables and plots of median profiles, concentrations will be set to missing if one of the following cases is true:

1. A concentration has been reported as ND (ie, not done) or NS (ie, no sample);
2. A deviation in sampling time is of sufficient concern or a concentration has been flagged as anomalous by the clinical pharmacologist.

Summary statistics will not be presented at a particular time point if more than 50% of the data are missing. For analysis of pharmacokinetic concentrations, no values will be imputed for missing data.

### **5.3.1.2. Pharmacokinetic parameters**

Whether actual or nominal PK sampling time will be used for the derivation of PK parameters will be determined by the results of interim PK analyses. If a PK parameter cannot be derived from a patient's concentration data, the parameter will be coded as NC (ie, not calculated). NC values will not be generated beyond the day that a patient discontinues.

In summary tables, statistics will be calculated by setting NC values to missing. Statistics will not be presented for a particular treatment if more than 50% of the data are NC. For statistical analyses (ie, analysis of variance), PK parameters coded as NC will also be set to missing.

If an individual patient has a known biased estimate of a PK parameter (due for example to a deviation from the assigned dose level), this will be footnoted in summary tables and will not be included in the calculation of summary statistics or statistical analyses.

### **5.3.2. Handling of incomplete dates**

#### **5.3.2.1. Disease history**

Incomplete dates for disease history (eg, initial diagnosis date, date of documented, locally advanced, inoperable or metastatic disease diagnosis, date of response or progression in prior treatment) will be imputed as follows:

- If the day is missing, it will be imputed to the 15th day of the month.
- If both day and month are missing and the year is prior to the year of the first study treatment, the month and day will be imputed as July 1st.
- If both day and month are missing and the year is same as the year of the first study treatment, the month and day will be imputed as January 1st.
- If the date is completely missing, no imputation will be performed.

#### **5.3.2.2. Adverse events**

Incomplete AE-related dates will be imputed as follows:

- If the AE onset date is missing completely, then the onset date will be replaced by the start of study treatment.
- If only the day part of the AE onset date is missing, but the month and year are equal to the start of study treatment, then the AE onset date will be replaced by the start of study treatment. For example, if the AE onset date is --/JAN/2015, and study treatment start date is 15/JAN/2015, then the imputed AE onset date will be 15/JAN/2015.
- If both the day and month of the AE onset date are missing but the onset year is equal to the start of study treatment, then the onset date will be replaced by the start of study treatment. For example, if AE onset date is --/--/2014, and study treatment start date is 19/NOV/2014, then the imputed AE onset date will be 19/NOV/2014.
- In all other cases the missing onset day or missing onset month will be replaced by 1.
- Incomplete stop date will be replaced by the last day of the month (if day is missing only), if not resulting in a date later than the date of patient's death. In the latter case the date of death will be used to impute the incomplete stop date.
- In all other cases the incomplete stop date will not be imputed. If stop date of AE is after the date of cut-off outcome of AE is ongoing at cut-off.

#### **5.3.2.3. Prior and concomitant medications**

Incomplete prior/concomitant medication dates will be imputed as follows:

- If the medication date is missing completely, then the medication date will be replaced by the start of study treatment.
- If the day of medication date is missing, but the month and year are equal to the start of study treatment, then the medication date will be replaced by the start of study treatment. For example, if the medication start date is --/JAN/2015, and study treatment start date is 15/JAN/2015, then the imputed medication start date will be 15/JAN/2015.

- If both the day and month of medication start date are missing but the start year is equal to the start of study treatment, then the medication date will be replaced by the start of study treatment. For example, if the medication start date is --/---/2014, and study treatment start date is 19/NOV/2014, then the imputed medication start date will be 19/NOV/2014.
- In all other cases the missing medication day or missing medication month will be replaced by 1.
- Incomplete stop date will be replaced by the last day of the month (if day is missing only), if not resulting in a date later than the date of patient's death. In the latter case the date of death will be used to impute the incomplete stop date.
- In all other cases the incomplete medication stop date will not be imputed.

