#### **6.5.2.2. Protocol deviations**

All protocol violations that impact the safety of the patients and/or the conduct of a study and/or its evaluation will be reported. These include:

- Patients who are dosed on the study despite not satisfying the inclusion criteria
- Patients who develop withdrawal criteria whilst on the study but are not withdrawn
- Patients who receive the wrong treatment or an incorrect dose
- Patients who receive an excluded concomitant medication
- Deviations from GCP

The identification of these and other CSR-reportable deviations will be based on the inclusion/exclusion criteria or other criteria presented in the protocol.

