##### **Combinations B, C and D**

The following analyses will be based on the safety analysis set by treatment group using the data from Phase 1b and from Phase 2 separately and for each combination.

**Concomitant medications** are medications, other than study drugs, which started prior to first dose date of study treatment and continued during the on-treatment period as well as those started during the on-treatment period.

Concomitant medications will be summarized from the ‘General Concomitant Medications’ eCRF page.

Summary of concomitant medications will include the number and percentage of patients by Anatomical Therapeutic Chemical (ATC) Classification level 2 and preferred term. A patient will be counted only once within a given drug class and within a given drug name, even if he/she received the same medication at different times. If any concomitant medication is classified into multiple ATC classes, the medication will be summarized separately under each of these ATC classes. The summary tables will be sorted on decreasing frequency of drug class and decreasing frequency of drug name in a given drug class. In case of equal frequency regarding drug class (respectively drug name), alphabetical order will be used. In case any specific medication does not have ATC classification level 2 coded term, it will be summarized under ‘Unavailable ATC classification’ category.

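### Missing AE onset and medication start dates are set to first dose without checking the stop date, so records that ended before treatment can be counted as TEAEs or concomitant medications

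*SAP*

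**What the plan says.** For medications, SAP 5.3.2.3 moves the start date to first dose in three cases:

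- The date is completely missing: "If the medication date is missing completely, then the medication date will be replaced by the start of study treatment".
- Only the day is missing: "If the day of medication date is missing, but the month and year are equal to the start of study treatment".
- Day and month are missing: "If both the day and month of medication start date are missing but the start year is equal to the start of study treatment".

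All other partial dates go to the first day or first month: "In all other cases the missing medication day or missing medication month will be replaced by 1".

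SAP 5.3.2.2 applies the same scheme to AE onset, beginning with "If the AE onset date is missing completely, then the onset date will be replaced by the start of study treatment". One of its worked examples reads "if AE onset date is --/--/2014, and study treatment start date is 19/NOV/2014, then the imputed AE onset date will be 19/NOV/2014". In both sections the stop date appears only in the rules for completing the stop date itself. A stop with the day missing goes to the last day of its month, limited by the date of death. A stop missing more than the day is not imputed.

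Classification then rests on the start. A TEAE is defined by an onset within the on-treatment period, which opens at first dose (SAP 3.5.1 and 6.6.1). Under SAP 6.5.4, concomitant medications are those begun earlier and continued into that period "as well as those started during the on-treatment period". The second group carries no condition on the stop date.

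**The concern.** Setting an unknown start to first dose is a conservative convention when timing relative to treatment is in doubt. A stop date before first dose removes that doubt: the record ended before treatment, whenever it began. The rule as written ignores that recorded fact and creates a start later than the stop.

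Because TEAE and concomitant status follow from the start, the impossible date decides the classification. SAP 6.5.4 describes a summary of concomitant medications only, so the classification also decides whether a medication is tabulated at all. The error runs one way: it can only add records to the TEAE and concomitant-medication tables.

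**Working it through.** **Inputs.** The start-date rules come from SAP 5.3.2.2 and 5.3.2.3, the on-treatment period and TEAE definition from 3.5.1, and the concomitant definition from 6.5.4. The SAP's examples give no stop dates, so those below are assumed for illustration.

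**Step 1: reproduce the SAP's examples.** --/JAN/2015 with first dose 15/JAN/2015 gives 15/JAN/2015. --/--/2014 with first dose 19/NOV/2014 gives 19/NOV/2014. Both match the SAP.

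**Step 2: add a stop date and apply the rules literally.** Difference = stop date − imputed start; a negative value is impossible. A record counts as on-treatment if its imputed start is on or after first dose.

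| Recorded start | First dose | Assumed stop | Imputed start | Difference (days) | Counted on-treatment |
|---|---|---|---|---|---|
| --/JAN/2015 | 15/JAN/2015 | 10/JAN/2015 | 15/JAN/2015 | −5 | Yes, wrongly |
| --/--/2014 | 19/NOV/2014 | 10/MAR/2014 | 19/NOV/2014 | −254 | Yes, wrongly |
| completely missing | 19/NOV/2014 | 05/NOV/2014 | 19/NOV/2014 | −14 | Yes, wrongly |
| --/DEC/2014 | 15/JAN/2015 | 09/JAN/2015 | 01/DEC/2014 | +39 | No, correctly |
| --/--/2013 | 19/NOV/2014 | 10/MAR/2014 | 01/JAN/2013 | +433 | No, correctly |
| completely missing | 19/NOV/2014 | 05/DEC/2014 | 19/NOV/2014 | +16 | Yes, acceptable |

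The first three rows are the three cases that move to first dose. The next two show that partial dates in an earlier month or year are handled correctly.

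**Step 3: partial stop dates.** With first dose 19/NOV/2014 and a completely missing start, a stop of --/OCT/2014 is imputed to 31/OCT/2014, before first dose, and the fault occurs. A stop of --/NOV/2014 is imputed to 30/NOV/2014, after first dose, and it does not.

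**Step 4: look for a correction elsewhere.** No other section returns such a record to pre-treatment. SAP 5.3.3.4 shows the missing safeguard for another variable. When the start of new anti-cancer therapy is completely missing, the imputed start is min[max(PD date + 1, last dose + 1), end date], so it cannot pass the end date.

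**Step 5: size.** The SAP gives no count of such records. A patient is counted once per SOC or PT (6.6.1) and once per drug class or drug name (6.5.4). The largest shift from one patient is therefore 1/n: 1/20 = 5 points in a cohort of 20, 1/35 = 2.9 points in Cohort A5, and 1/12 = 8.3 points in a Phase 1b dose level of 12. It is zero for any row in which the patient already has another qualifying record.

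**Step 6: apply the remedy, min(current rule, stop date).** The first three rows become 10/JAN/2015, 10/MAR/2014 and 05/NOV/2014, all before first dose. The other rows do not change.

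**The case against.** The strongest defence is that imputing to first dose is usual and errs toward over-reporting safety events, that the affected tables are descriptive, and that such records may be rare in cleaned eCRF data. SAP 5.3.1 also requires imputed values to be flagged in listings, so someone reading a listing could see the conflict with the recorded stop. All of this stands as a limit on importance. It does not rescue the rule, because a known earlier stop leaves nothing to be conservative about, and a flag in a listing does not change a count in a table.

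Several stronger readings are tempting but not supported:

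- **Every partial date in the year of first dose is affected.** It is not. With only the day missing, month and year must both match. A start of --/MAR/2014 with first dose 19/NOV/2014 becomes 01/MAR/2014 and stays pre-treatment.
- **False protocol deviations would follow.** SAP 6.5.2.2 does list "Patients who receive an excluded concomitant medication", but it ties identification to criteria in the protocol. It does not say that imputed dates or the 6.5.4 classification are used.
- **Prior anti-cancer drugs would appear as concomitant.** These are collected on separate prior-therapy pages (SAP 6.5.1.4), while the 6.5.4 summary draws on the general concomitant medications page.
- **Infusion-related reactions would be inflated.** A negative duration does pass the Appendix 2 limit of at most 2 days from onset to end, but for signs and symptoms the recorded timing must still be during or after infusion.

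**Conclusion.** The rule is wrong as written within a defined scope. It misclassifies a record when the start is completely missing, lacks only the day in the month and year of first dose, or lacks day and month in the year of first dose, and the stop date (complete or imputed to month end) is before first dose. For those records the result follows with certainty from the SAP's text.

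The size is uncertain. The number of records cannot be derived from the SAP and may be small. The 5 points for a cohort of 20 is a ceiling for one patient in one row; it should not be read as an expected bias. Confirmed ORR and its exact tests do not use these imputations, and no effect on protocol deviations is shown. This is a correction worth making to safety and medication tables, and it does not threaten the trial's primary conclusions.

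**What to change.** In both 5.3.2.2 and 5.3.2.3, add a condition ahead of the three rules that move a date to first dose:

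- Impute to the start of study treatment only if the stop date is missing, ongoing, or on or after the start of study treatment.
- Otherwise, imputed start = min(date from the current rule, stop date), in line with the use of the end date in 5.3.3.4.
- For this check, use the stop date as recorded or as imputed to month end, and treat a year-only stop as 31DECYYYY, also as in 5.3.3.4. Without this, a completely missing start with a stop in 2013 and first dose in 2014 would still be moved to first dose.

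Records caught by the condition are then classified as prior medications or as AEs that are not treatment-emergent. The conservative rule remains for all records whose timing is really unknown. The cost is a short addition to two sections and one programming condition. It needs no new data.

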#### **5.3.2.4. Exposure**

No imputation will be done for first dose date. Date of last dose of study drug, if unknown or partially unknown, will be imputed as follows:

- If the last date of study drug is completely missing and there is no End of Treatment eCRF page and no death date, the patient should be considered to be ongoing and use the cut-off date for the analysis as the last dosing date
- If the last date of study drug is completely or partially missing and there is EITHER an End of Treatment eCRF page OR a death date available (within the cut-off date), then imputed last dose date is:
  - = 31DECYYYY, if only Year is available and Year < Year of min (EOT date, death date)
  - = Last day of the month, if both Year and Month are available and Year = Year of min (EOT date, death date) and Month < the month of min (EOT date, death date)
  - = min (EOT date, death date), for all other cases.

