#### **Start and end dates of study treatment:**

The date/time of first dose of study treatment in a combination group is the earliest date/time of the first non-zero dose date/time for the study drugs in the combination.

The date/time of last dose of study treatment in a combination group is the latest date/time of the last non-zero dose date/time for the study drugs in the combination.

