### **5.2.7. Definition of on-treatment period**

Safety endpoints will be summarized based on the on-treatment period unless otherwise specified.

On-treatment period is defined as the time from the first dose of study treatment through minimum (30 days + last dose of study treatment, start day of new anti-cancer drug therapy – 1 day).

Safety data collected outside the on-treatment period as described above will be listed and flagged in listings but not summarized.

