    YYYY = Year of min [max(PD date + 1, last dose of study treatment + 1), end date of new anti-cancer therapy], AND

```
MMM = Month of min [max(PD date + 1 day, last dose of study treatment + 1
day), end date of new anti-cancer therapy]
THEN
    imputed start date = min [max(PD date + 1 day, last dose of study treatment + 1
day), end date of new anti-cancer therapy]);
ELSE IF
    YYYY = Year of min [max(PD date + 1, last dose of study treatment + 1), end
date of new anti-cancer therapy], AND
    MMM > Month of min [max(PD date + 1 day, last dose of study treatment + 1
day), end date of new anti-cancer therapy]
THEN
    imputed start date = 01 MMM YYYY;
ELSE IF
    YYYY < Year of min [max(PD date + 1, last dose of study treatment + 1), end
date of new anti-cancer therapy]
THEN
    imputed start date = DAY (Last day of MMM) MMM YYYY;
ELSE IF
    YYYY > Year of min [max(PD date + 1, last dose of study treatment + 1), end
date of new anti-cancer therapy]
THEN
    imputed start date = 01 MMM YYYY.
```

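### Last-dose imputation (SAP 5.3.2.4) overrides a recorded month and year when they fall in a calendar year before end of treatment or death

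*SAP*

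**What the plan says.** SAP Section 5.3.2.4 applies three branches when a last-dose date is wholly or partly missing and an EOT page or a death date exists within the cut-off:

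1. Year only, earlier year: "31DECYYYY, if only Year is available and Year < Year of min (EOT date, death date").
2. Year and month: "Last day of the month, if both Year and Month are available and Year = Year of min (EOT date, death date"), with the further condition that the recorded month precedes the month of that minimum.
3. Everything else: "min (EOT date, death date), for all other cases".

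Section 5.3.3.4 imputes the start of new anti-cancer therapy. For year and month known with an earlier year it has its own branch: "imputed start date = DAY (Last day of MMM) MMM YYYY".

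Section 5.2.7 ends the on-treatment period at the "minimum (30 days + last dose of study treatment, start day of new anti-cancer drug therapy" less one day). Section 3.4.1 takes the last dose of study treatment as the latest last non-zero dose across the drugs in the combination.

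**The concern.** The three branches leave one case without a rule of its own: day missing, month and year recorded, and the year before that of min(EOT, death). Branch 1 excludes it because more than the year is known. Branch 2 excludes it because the years differ. The catch-all then assigns a date in a month and year that the record contradicts.

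The last-dose date is used in several places:

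- the on-treatment period, and through it treatment-emergent status and the on-treatment laboratory and ECG summaries (Sections 3.5.1, 5.2.7, 6.6.1, 6.6.5, 6.6.7);
- deaths within 30 days of last dose (Section 6.6.2);
- the 90-day window for immune-related events (Appendix 1, Table 15, step 2);
- duration of exposure for every drug (Sections 6.5.3.1 to 6.5.3.5);
- the CMP-001 relative dose intensity denominator (Section 6.5.3.5);
- an imputed start of new anti-cancer therapy (Section 5.3.3.4).

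A date that is too late lengthens each window. Where death is the earlier reference date, last dose is set equal to death, and the death then counts as within 30 days whatever dosing month was recorded.

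**Working it through.** The SAP gives no figure to reproduce, so the check applies the branches as written to partial dates. All calendar dates below are assumed for illustration.

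**Main example.** Recorded last dose --/NOV/2017; min(EOT, death) = 20FEB2018.

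- Branch 1: not met, because the month is known.
- Branch 2: not met, because 2017 ≠ 2018.
- Branch 3: 20FEB2018.
- Latest date the record allows: 30NOV2017. Excess = 31 (December) + 31 (January) + 20 (February) = 82 days. This is a lower bound. Had the true date been 01NOV2017, the excess would be 82 + 29 = 111 days.

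Effect on derived quantities, if this date becomes the last dose of study treatment:

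| Quantity | Rule as written | Last day of recorded month |
|---|---|---|
| Last dose | 20FEB2018 | 30NOV2017 |
| On-treatment end (+30 days, no new therapy) | 22MAR2018 | 30DEC2017 |
| Immune-related window end (+90 days) | 21MAY2018 | 28FEB2018 |
| Avelumab exposure duration | 82/7 = 11.7 weeks longer | reference |

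**Range.** The excess depends only on the gap from the end of the recorded month to EOT or death:

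| Recorded | min(EOT, death) | Rule as written | Last day of recorded month | Excess (days) |
|---|---|---|---|---|
| DEC2017 | 02JAN2018 | 02JAN2018 | 31DEC2017 | 2 |
| DEC2017 | 10JAN2018 | 10JAN2018 | 31DEC2017 | 10 |
| NOV2017 | 10JAN2018 | 10JAN2018 | 30NOV2017 | 41 |
| OCT2017 | 10JAN2018 | 10JAN2018 | 31OCT2017 | 71 |
| JUN2017 | 15MAR2018 | 15MAR2018 | 30JUN2017 | 258 |

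**Controls.** These come out the same under the present and the repaired rule:

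- OCT2017 with EOT 10DEC2017 gives 31OCT2017.
- 2017 alone with EOT 10JAN2018 gives 31DEC2017.
- JAN2018 with EOT 10JAN2018 gives 10JAN2018.

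The second control shows the inconsistency. For the same EOT of 10JAN2018, 2017 alone gives 31DEC2017, but NOV2017 gives 10JAN2018. Adding the month moves the imputed date out of the recorded year.

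**CMP-001 relative dose intensity.** Section 6.5.3.5 sets the denominator at 40 mg if last minus first dose date is at most 25 days, 30 mg for 26 to 50 days, and 20 mg otherwise. Assume a first dose on 06NOV2017, four weekly 10 mg doses in November, one cycle, and the main example's partial date.

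- Actual intensity: 40 mg / (4 weeks/4) = 40 mg per cycle.
- Last day of recorded month: span 24 days, denominator 40, result 100 × 40/40 = 100%.
- Rule as written: span 24 + 82 = 106 days, denominator 20, result 100 × 40/20 = 200%.

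**The case against.** The gap itself is hard to dispute; the case on the other side is about reach.

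- **The trigger is narrow.** The day must be missing, month and year must be present, and EOT or death must fall in a later calendar year. The SAP works from cleaned eCRF data, and its cycle and infusion-reaction rules rely on exact dosing dates, so partial last-dose dates should be uncommon. The SAP gives no frequency. This stands.
- **The size varies.** Eighty-two days is one assumed case; a DEC2017 record with EOT on 02JAN2018 is off by only 2 days. This stands, which is why a range is given.
- **The consequences are conditional.** The on-treatment period moves only if the imputed date is the latest across the combination, it is capped by new anti-cancer drug therapy, and an event must fall in the added interval. This stands for treatment-emergent events. The cap, however, does not apply to deaths within 30 days, and Table 15 states that the 90-day window runs regardless of new therapy.
- **Other analyses are barely touched.** Dose intensity for the four IV drugs uses cycle start dates, not the last-dose date. The primary response analysis and the DLT-evaluable set do not use last dose directly; response could be reached only through a new-therapy start date that is itself missing or partial. This also stands.

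None of this makes the imputed date defensible. It cannot be read as a conservative choice, because the year-only branch and Section 5.3.3.4 both keep to the recorded period.

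**Conclusion.** The rule is wrong as written. Every record that reaches this path gets a date its own month and year exclude, and nothing else in the SAP corrects it. The excess runs from a couple of days to many months (2 to 258 days in the assumed cases).

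Probably few patients are affected, and the effect falls on safety and exposure summaries. Cohorts are small, though: one misclassified death or adverse event moves a percentage by 1/35 = 2.9 points in a cohort of 35 and by 1/20 = 5 points in a cohort of 20. The conclusion rests on a literal reading of Section 5.3.2.4; the sizes rest on the assumed dates. It should be corrected, although the primary endpoints do not depend on it.

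**What to change.** Reword the second branch of Section 5.3.2.4 so that it returns the last day of the recorded month when month and year are available and either:

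- Year < Year of min(EOT, death), or
- Year = Year of min(EOT, death) and Month < Month of min(EOT, death).

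This matches the logic of Section 5.3.3.4. It changes no same-year or year-only case and costs one line of SAP text and one condition in the program. A short listing of partial last-dose dates would show whether any patient is affected.
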